4.1.1 Study design for Control Cohort

Previous experience with clinical trials designed for IH treatment and performed in the US have demonstrated that parents are unlikely to enroll in double-masked, randomized, placebo- controlled studies. Therefore, two different strategies will be implemented to obtain age- matched control data. One strategy will include sharing of data and clinical photographs from two other completed randomized, placebo controlled studies in infants with IH. The patients in these studies are of similar age to our study and present similar IH characteristics. For the purpose of this study, the control group and the placebo groups from the two similar studies will serve as the untreated control cohort in our study.

[figure not shown]
The first study identified is a recently completed prospective, single-center, double-masked, randomized, placebo-controlled efficacy study in Barcelona, Spain (Efficacy and safety of topical administration of timolol maleate 0.5% solution in the treatment of Child Proliferative Hemangioma Early Stage Surface. Randomized Controlled Study). This study has enrolled a total of 70 patients, 35 randomized to 0.5% timolol BID and 35 to placebo BID for 6 months. (EudraCT Number: 2013-005199-17). In addition, photographs from a second previously published double-masked, randomized, placebo-controlled trial (Australian and New Zealand Clinical Trials Registry Number: ACTRN12610001069044) are anticipated to be provided for analysis.²⁰ These studies are anticipated to provide paired clinical photographs of approximately 35 placebo-treated patients through up to 180 days following baseline.

As a secondary strategy, approximately 10 infants who are eligible for this study based on inclusion and exclusion criteria, but whose parents decide not to treat the IH, will be enrolled and also serve as a part of the untreated control cohort.

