5.3.7 Randomization of Participants in the Non-intervention Arm

If at any time during the study the parents of an infant in the non-intervention arm change their mind and want timolol maleate GFS therapy, the infant will be randomized for participation in the study if there is a need for additional enrolled subjects and the infant meets the inclusion criteria and none of the exclusion criteria at the time of first dose.

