6.6 Efficacy Assessment Using Centralized VAS

Efficacy will be determined at the end of the study by centralized evaluation of five standardized digital photographs (taken by investigators at each visit). All collected images from both arms of the study and the untreated control group will be evaluated in a masked fashion by expert pediatric dermatology Raters. Each study site will be given photographic equipment and a minimum of two individuals at each site will be trained to capture standardized photographs. Detailed information will be in the MOP and the photography vendor's User's Manual on how to take the pictures of the infant's hemangioma in order to obtain a systematic and consistent approach. All study and control photographs will undergo a centralized/standardized color calibration by the photography vendor before they are sent for assessment by the Raters. Two expert Raters and one Adjudicator will be trained on the Visual Analog Scale (VAS), how to recognize change in volume and color, and in the comparison of the hemangioma from baseline to study endpoint. However, assessment will initially be completed by 2 of the Raters. Adjudication by the Adjudicator will occur in a case of disagreement between the two Raters (see Rater's User's Manual). For the purpose of this study, a disagreement will be defined as a difference in both Raters' assessment concerning the treatment response categories on the VAS scale. Raters will use the VAS (see Section 10.1) to rate changes in volume and changes in color separately. Raters will be masked to both treatment assignment and timing of the digital photograph. Interreader and intrareader reliability of the Raters will be assessed prior to evaluation of study infants. The scores of the centralized Raters will be used to determine the success or failure of timolol therapy to obtain partial or complete regression of hemangioma in each study infant.

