4. Absolute change in hemangioma dynamic complication scale from Day 0 to end of study within each treatment arm.
5. Assess time to partial response by comparing baseline to day 30, day 60, day 120 and day 180 in both treatment arms.
6. Absolute change in IH-QoL score scale from Day 0 to end of study within each treatment arm.

Secondary **safety** endpoints are the rate of serious adverse events and adverse events of special interest (Section 8.1.2) from randomization to Day 180 in infants treated with topical timolol maleate (0.25% and 0.5%) GFS for the treatment of infantile hemangioma.

Exploratory Endpoints:

Exploratory PK endpoints include estimation of PK parameters such as clearance (CL), volume of distribution (V), area under the curve (AUC), and maximum concentration (C_{max}), as possible.

The relationship between different hemangioma characteristics and plasma concentrations may also be described as an exploratory endpoint.

Treatment Failure for Partial Response in Hemangioma Color or Volume

The infant will be considered a treatment failure for the primary endpoint of partial response of VAS-volume or the secondary endpoint of partial response of VAS-color from baseline to Day 180 if any of the following conditions are met:

1. Partial response not achieved at the Day 180 visit in infants who complete the 180-day treatment period.
2. Infant withdrawn from masked treatment due to progressive disease. This will include participants randomized to the 0.25% treatment arm and switched to the 0.5% treatment arm.
3. Ulceration of the target hemangioma after initiation of masked treatment.
4. Infant withdrawn from study treatment due to safety concerns.
5. Study drop-out or loss to follow-up after the 30-day visit and before the 180-day visit for reasons other than progressive disease, ulceration, or safety concerns without having achieved partial response at the last study visit before drop-out.

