10.2 Study Hypotheses Tested

For the primary analyses of treatment efficacy, let p_{RC} be the proportion with partial or greater response in hemangioma volume for the control cohort, p_{R25} the proportion with partial or greater response in hemangioma volume for the 0.25% arm, and p_{R50} the proportion with partial or greater response in hemangioma volume for the 0.5% arm. The following set of hypotheses will be assessed:

Hypothesis 1 (H_1): The partial response proportion in the 0.5% arm is greater than the partial response proportion in the control cohort.

Null hypothesis H_{10} : $p_{R50} \leq p_{RC}$

Alternative hypothesis H_{1A} : $p_{R50} > p_{RC}$

Hypothesis 2 (H_2): The partial response proportion in the 0.25% arm is greater than the partial response proportion in the control cohort.

Null hypothesis H_{20} : $p_{R25} \leq p_{RC}$

Alternative hypothesis H_{2A} : $p_{R25} > p_{RC}$

A secondary efficacy hypothesis comparing treatment arms will also be tested:

Secondary efficacy hypothesis (H_3): The partial response proportion in the 0.25% arm is not equal to the partial response proportion in the 0.5% arm.

Null hypothesis H_{30} : $p_{R25} = p_{R50}$

Alternative hypothesis H_{3A} : $p_{R25} \neq p_{R50}$

The $\alpha=0.05$ level will be used for hypothesis testing. Hypotheses will be tested with chi-square or Fisher's exact tests. A Bonferroni multiplicity correction will be applied to the α level for the primary hypotheses. Response proportions will be further compared between groups using the odds ratio or estimated differences in proportions and corresponding confidence interval estimates.

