10.4 Analysis Plan

10.4.1 Population for Analysis

All randomized infants who received study dose and non-randomized participants enrolled in the untreated control cohort will be included in the intent-to-treat population. The primary analysis will use the intent-to-treat population with treatment group determined by randomization assignment.

All infants enrolled and receiving at least one dose of timolol therapy will be included in the safety population and the safety analysis. All infants who had at least one interpretable PK sample will be included in the PK analysis.

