10.4.4 Efficacy Analysis

Key efficacy endpoints are summarized in Section 10.1. Chi-square or Fisher's exact tests will be used to test response proportion hypotheses at study end. Response proportions will be further compared via odds ratio, difference in proportion, and confidence interval estimates.

Further adjusted analyses taking into account postnatal age, gestational age, and other baseline or demographic covariates of interest via logistic regression will be performed. Differences between studies used for the control data will be assessed.

As discussed in Section 10.1, randomized participants who switch to unmasked treatment with timolol maleate 0.5% GFS due to disease progression will be classified as treatment failures in the primary analysis. VAS scores following the switch to unmasked treatment will be analyzed as a secondary analysis. Both the VAS assessment of change from study baseline and change in VAS score from the time of treatment switching will be summarized in this secondary analysis. The duration of unmasked treatment will be summarized. Partial response of color or volume from the start of randomized treatment will be evaluated in participants who switch treatment using data collected after the treatment switch.

Additional secondary efficacy variables for analysis between randomized treatment arms include severity of the hemangioma, time to partial response, and quality of life measurement variables. Absolute change in overall severity will be measured via hemangioma dynamic complication scale from baseline to Day 180 within each treatment arm. Absolute change in quality of life will be measured via IH-QoL score scale from baseline to Day 180 within each treatment arm. Linear mixed effects modeling techniques will be used to analyze changes in the quantitative VAS scores, severity scale, or quality over time, and adjustments for demographic covariates of interest will be considered.

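### Failure rules 2 and 3 for the primary endpoint do not reach the roughly 10 non-intervention controls, so the same ulceration or progression course can be failure in a treated infant and response in a control (minor; bias against timolol)

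*Combined protocol and SAP*

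**What the plan says.** Section 10.1 lists five conditions, any one of which makes an infant a treatment failure for partial response. Rule 2 is "Infant withdrawn from masked treatment due to progressive disease", including a switch from 0.25% to 0.5%. Rule 3 is "Ulceration of the target hemangioma after initiation of masked treatment". Rule 4 is withdrawal from study treatment for safety. Section 10.4.4 restates the switch rule: "randomized participants who switch to unmasked treatment with timolol maleate 0.5% GFS due to disease progression will be classified as treatment failures".

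The untreated control cohort has two sources (section 4.1.1): about 35 placebo infants from two external double-masked trials, and about 10 infants eligible for this study "but whose parents decide not to treat the IH, will be enrolled and also serve as a part of the untreated control cohort". Section 10.4.1 says that "non-randomized participants enrolled in the untreated control cohort will be included in the intent-to-treat population", and section 10.2 defines the comparator in H1 and H2 as "the proportion with partial or greater response in hemangioma volume for the control cohort". Scoring is common to all groups: "All collected images from both arms of the study and the untreated control group will be evaluated in a masked fashion" (section 6.6).

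**The concern.** The photographs are read the same way in every group, so any difference in scoring comes from the override rules. Rules 2 and 3 presuppose masked treatment, which non-intervention infants never receive, and no equivalent rule is written for them. Part of the control group in H1 and H2 is therefore scored more leniently than the arms it is compared with. That raises the control proportion relative to the treated ones, understates the timolol effect and costs some power.

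The existing sensitivity analyses in section 10.1 concern drop-out. They would not show a control who ulcerated, or was treated outside the study, and stayed to Day 180.

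**Working it through.** **1. Same course, two scores.**

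| Course, with >20% volume reduction at Day 180 | Treated infant | Non-intervention infant |
|---|---|---|
| Target lesion ulcerates | Failure (rule 3) | Responder: rule 3 needs masked treatment |
| Progresses; treated infant is withdrawn or switched, control starts therapy outside the study | Failure (rule 2; 10.4.4) | Responder: rule 2 and 10.4.4 need masked or randomized treatment |

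**2. Do other sections close the gap?** Section 5.3.7 lets a control be randomized only "if there is a need for additional enrolled subjects and the infant meets the inclusion criteria and none of the exclusion criteria" at first dose. Those criteria include age 0–84 days (5.2.1), so an older control cannot take this route. Section 7.4 bars oral or IV beta blockers, oral or IV corticosteroids and topical corticosteroids on the lesion, and permits all other drugs. It does not name topical timolol obtained outside the study. These sections narrow the therapy case without closing it, and they do not touch ulceration. A control who leaves because of progression or ulceration falls under no numbered rule, since rule 5 excludes those reasons. Sections 10.1 and 10.4.1 together suggest a non-responder kept in the denominator, but the plan does not say so.

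**3. Reproduce the planned power.** Inputs from section 10.3: 45 per treated arm, 35 controls, response 0.15 (control), 0.45 (0.25% arm) and 0.50 (0.5% arm); stated power 93% (H1) and 85% (H2). I summed exact binomial probabilities over all outcomes where the pooled chi-square statistic favours timolol with z > 1.96 (one-sided 0.025). This gives 92.9% and 84.3%. Two-sided 0.025 gives 87.9% and 76.2%, which does not match. One-sided 0.025 is therefore inferred, not stated. It has the same critical value as an uncorrected two-sided 0.05, so the match cannot separate those two. With 45 controls (35 + 10), power is 96.1/89.8%. Section 10.3 does not say whether its 35 include the 10.

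**4. Size of the effect.** Let r be the share of would-be responders who have a rule 2 or 3 event. The documents give no value; 5%, 10% and 20% are assumptions.

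- *Gross*: planned rates are before the rules. Common scoring multiplies every rate by (1 − r); literal scoring leaves the 10 non-intervention infants at 0.15.
- *Net*: planned rates already include the rules. Treated arms stay at 0.50/0.45 and placebo infants at 0.15; the 10 are at 0.15/(1 − r).

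Power for H1/H2 (%), 45 controls:

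| r | Gross: common | Gross: literal | Loss, gross (points) | Loss, net (points) |
|---|---|---|---|---|
| 5% | 94.7/87.6 | 94.5/87.1 | 0.3/0.5 | 0.2/0.4 |
| 10% | 93.0/85.1 | 92.4/84.0 | 0.6/1.1 | 0.4/0.9 |
| 20% | 88.7/79.2 | 86.7/76.3 | 2.0/2.9 | 1.0/2.1 |

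Variants: if the 10 are among 35 controls, the gross losses are 0.5/0.7, 1.1/1.6 and 3.1/4.0 points. With a two-sided 0.025 test and 45 controls they are 0.4/0.7, 1.0/1.5 and 2.7/3.4.

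**5. In infants (gross case).** Expected extra control responders = 10 × 0.15 × r = 0.08, 0.15 or 0.30. The chance of at least one = 1 − (1 − 0.15r)^10 = 7%, 14% or 26%; of two or more, at most 3.5%. The expected shift in the control proportion is 0.15 × r × 10/45 = 0.17, 0.33 or 0.67 percentage points, against planned differences of 30 and 35. One extra responder is 1/45 = 2.2 points; raising the control rate by that much takes power from 96.1/89.8 to 92.9/83.7.

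**6. Type I error.** With equal true response of 0.15 in all groups and 45 controls, the exact rate is about 0.028 under common rules and 0.026, 0.025 and 0.023 under literal scoring for the three values of r. It falls.

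**The case against.** The strongest reply is that this hardly matters. An affected control must ulcerate, or progress and be treated outside the study, and still shrink by more than 20%; fewer than one such infant is expected. The bias is conservative. The success rates in section 10.3 are for an endpoint that already includes the failure rules, so the smaller net losses are arguably the natural ones. All of this stands and is why the point is minor.

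The plan also has partial cover. Section 10.4.4 evaluates VAS-based response after the switch in treated infants who change to open-label 0.5%, which is how controls are scored, so the switch asymmetry can be partly inspected. Nothing comparable covers ulceration, or therapy outside the study in controls who stay to Day 180. The mixed models of quantitative VAS do not depend on the failure rules, but the plan does not say that they include controls.

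A literal reading can be pushed too far. Rule 1 also refers to completing the treatment period, so it does not name these controls either. The sensible reading is that they are scored by the general VAS definition, which leaves rules 2 and 3 as the difference. Rule 4 has no counterpart in an untreated infant and is not part of the defect.

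A reader might infer that the rules miss the external placebo infants too, which at r = 20% with 45 controls would cost 10.3/14.0 points. The documents do not support that: those infants come from double-masked trials, so the words masked treatment can cover them. What the plan leaves open is whether the rules are meant to apply to them.

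**Conclusion.** The point holds as a minor defect: rules 2 and 3 score the compared groups unequally on the primary endpoint, for about 10 infants. With 45 controls the loss of power for H1/H2 lies between 0.2/0.4 and 2.0/2.9 points across the net and gross readings, and reaches about 3.1/4.0 if only 35 controls include the 10. These figures rest on assumed event shares of 5–20% and an inferred one-sided 0.025 test.

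A reader might infer a risk of a false positive finding, or a seriously weakened primary comparison. Neither follows. The bias runs against timolol, type I error does not rise, and the most likely outcome is that no control is affected. The reason to act is that the rule should be settled before the data are seen, at almost no cost.

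**What to change.** In section 10.1, for scoring H1 and H2:

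- Word rule 3 as ulceration of the target lesion after baseline, in any group.
- Extend rule 2 so that a control who progresses and leaves the study, or starts other hemangioma therapy, is scored as a failure and stays in the denominator.
- Leave rule 4 for infants on study drug or placebo.
- State that the rules apply to external placebo infants where disposition data exist, and report how many cannot be classified.
- Add one sensitivity analysis that scores all groups on the Day 180 central VAS alone.

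The cost is a few sentences and one small analysis. For non-intervention infants, photographs and concomitant medications are already collected (6.4.2), and Table 6-1 footnote 6 requires the complication scale, which has an ulceration item, for all participants. Some external placebo infants may remain unclassifiable if their trials cannot supply disposition data.

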Partial response will not be evaluated in participants who drop-out from the study for reasons other than progressive disease, ulceration, or safety concerns or are lost to follow-up before the 30-day visit. Sensitivity analyses will be performed to assess the impact of assumptions made to account for drop-out on the primary analysis. This will include summaries of partial response that exclude participants who withdrew for reasons other than lack of efficacy. Other methods, such as multiple imputation, may be considered based on drop-out rates and cause of missingness.

In addition to the assessments of partial response through the 180-day visit, the proportion of participants who achieve partial response through each study visit will be summarized. The number of participants with partial response before but not at the 180-day visit will be summarized.

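### No committed analysis puts early drop-outs back into the intent-to-treat primary analysis, and the one committed sensitivity analysis excludes further infants, including, as worded, safety failures

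*Combined protocol and SAP*

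**What the plan says.** Section 10.4.1 defines the primary set: "All randomized infants who received study dose and non-randomized participants enrolled in the untreated control cohort will be included in the intent-to-treat population". It continues: "The primary analysis will use the intent-to-treat population with treatment group determined by randomization assignment".

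Section 10.1 then decides who has an outcome within that set.

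- **Failures whatever the timing.** Withdrawal from masked treatment for progression (item 2), "Ulceration of the target hemangioma after initiation of masked treatment" (item 3) and "Infant withdrawn from study treatment due to safety concerns" (item 4).
- **Other drop-outs after the 30-day visit (item 5).** These are failures only if they left "without having achieved partial response at the last study visit before drop-out". An infant responding at the last visit is therefore not a failure.
- **Other drop-outs and losses before the 30-day visit.** "Partial response will not be evaluated in participants who drop-out from the study for reasons other than progressive disease, ulceration, or safety concerns", and the same holds for infants lost to follow-up before that visit.

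Section 10.1 promises sensitivity analyses for the drop-out assumptions. The one it commits to is a set of summaries that "exclude participants who withdrew for reasons other than lack of efficacy". Other methods, with multiple imputation as the example, depend on the amount and cause of drop-out. Section 10.3 randomises 100 infants to obtain 90 evaluable, allowing up to 10% with unevaluable response.

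**The concern.** Two things do not fit together.

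First, the label promises that every randomised and dosed infant is analysed, but some of them contribute neither a success nor a failure. They leave the denominator because of something that happened after randomisation.

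Second, the committed check does not address that choice. It starts from the reduced set and excludes more infants. A safety withdrawal is, in ordinary language, a withdrawal for a reason other than lack of efficacy, so the check discards infants whose outcome the plan has already fixed as failure. Ulceration withdrawals may go the same way, since ulceration is listed separately from progression and leads to withdrawal from study drug under Section 5.3.4.

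This matters more here than in a trial with a randomised placebo arm. The control cohort is non-randomised and comes mostly from placebo groups of other trials (Section 4.1.1), so exclusions in the timolol arms have no concurrent randomised counterpart. Section 2.1 says the results may be used in labelling negotiations.

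**Working it through.** **Inputs.** Section 10.3: control response 0.15 with 35 evaluable; 0.45 (0.25% arm) and 0.50 (0.5% arm) with 45 evaluable each; up to 10% of 100 randomised unevaluable, so about 5 of 50 per arm. Section 10.2: alpha 0.05 with a Bonferroni correction over two primary hypotheses, so 0.025 each; the hypotheses are written one-sided.

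**Reproducing the plan's power.** For the pooled test at one-sided 0.025,

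power = Φ{[(pT − pC) − 1.96·s0] / s1}, with s0 = √[p̄(1 − p̄)(1/nT + 1/nC)] and s1 = √[pT(1 − pT)/nT + pC(1 − pC)/nC].

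- 0.5% arm: p̄ = (22.5 + 5.25)/80 = 0.347, s0 = 0.1073, s1 = 0.0959; (0.35 − 0.2103)/0.0959 = 1.457; power 92.7%.
- 0.25% arm: p̄ = (20.25 + 5.25)/80 = 0.319, s0 = 0.1050, s1 = 0.0956; (0.30 − 0.2058)/0.0956 = 0.985; power 83.8%.

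Summing the exact binomial probabilities over the same rejection region gives 92.9% and 84.3%. The plan states 93% and 85%, so its basis is one-sided 0.025 per test. (Two-sided 0.025 would give 87.3% and 75.0%.) The randomised number follows from 90/0.90 = 100.

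**Putting the early losses back as non-responders.** With u unevaluable per arm, the rate becomes p × (50 − u)/50 on a denominator of 50. Control stays at 0.15 of 35.

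| Unevaluable per arm | Rates (0.5% / 0.25%) | Power, normal approximation | Power, exact sum |
|---|---|---|---|
| none (45 analysed) | 0.500 / 0.450 | 92.7% / 83.8% | 92.9% / 84.3% |
| 1 of 50 | 0.490 / 0.441 | 92.5% / 83.3% | 92.7% / 83.8% |
| 2 of 50 | 0.480 / 0.432 | 91.0% / 81.0% | 91.3% / 81.6% |
| 5 of 50 | 0.450 / 0.405 | 85.3% / 73.2% | 85.8% / 74.0% |

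**What the committed exclusion does.** The documents give no rate of safety or ulceration withdrawal, so these counts are assumptions. If s such failures among 45 are removed, the rate is 45p/(45 − s):

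| s removed | from 0.50 | from 0.45 |
|---|---|---|
| 1 | 0.511 | 0.460 |
| 2 | 0.523 | 0.471 |
| 3 | 0.536 | 0.482 |
| 5 | 0.562 | 0.506 |

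The same exclusion also removes later drop-outs whom item 5 does not count as failures. With 22.5/45 = 0.50 and 5 infants excluded, r of them responders, the rate is (22.5 − r)/40: 0.562 for r = 0, 0.512 for r = 2, 0.487 for r = 3 and 0.438 for r = 5. It falls when the response share among those excluded exceeds the arm's own rate. In none of these cases do the early losses re-enter the denominator.

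**The case against.** **The primary analysis is already strict.** Progression, switching to open label, ulceration and safety withdrawal are failures even before Day 30. This stands, and it confines the gap to other-reason early drop-outs and losses.

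**The exclusion analysis tests something real.** A reader might infer that every check in the plan favours timolol. The text does not support that. Removing last-visit responders tests a favourable feature of item 5 and can lower the rate, and multiple imputation is also mentioned. What remains is that imputation is optional and that the exclusion cannot test the omission of early losses.

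**Removal of ulceration failures is not a stated rule.** A reader might infer that it is. The plan defines neither *withdrew* nor *lack of efficacy*. The second could be meant to cover ulceration. The first could mean leaving the study, and under Section 5.3.4 infants taken off drug may keep attending visits and being photographed. On that reading some safety withdrawals would stay in too. This stands as a reason to fix the wording.

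**The power loss is a ceiling and treats one side only.** The 10% is a maximum, and Section 5.3.1 allows extra enrolment if more than 10 treated infants withdraw by Day 30. If the 35 controls were themselves evaluable out of 39 (an assumption), the control rate would be 5.25/39 = 0.135. Power at the full allowance would then be about 91%/82% by the normal approximation. This stands, so the remedy must cover controls. Extra enrolment replaces numbers but does not return the early losses to the analysis.

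**The finding might survive anyway.** In an assumed example, 20 responders of 45 become 20/50 when 5 unevaluable infants are counted as failures. Against 5/35, one-sided Fisher p = 0.009, still below 0.025. So the documents do not show that a positive result would be overturned.

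**Conclusion.** The point holds in a limited form. Some randomised and dosed infants have no outcome in an analysis labelled intent-to-treat. The only committed sensitivity analysis is a further exclusion which, on its plain wording, removes safety withdrawals already classed as failures and may remove ulceration withdrawals. No committed analysis tests the assumption that early losses can be ignored.

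If those infants are counted as non-responders, the assumed rates fall by 5.0 and 4.5 percentage points and power falls to about 86%/74% at the plan's maximum. With 2 per arm, power is about 91%/81–82%. These figures rest on the response rates in Section 10.3, one-sided 0.025 per test, and control fixed at 35 evaluable. The effect of the exclusion cannot be sized from the documents, and its direction depends on who is excluded. This is a worthwhile, cheap correction to the plan and does not show that its conclusion would be biased in a known direction.

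**What to change.** In Section 10.1:

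1. Commit to a sensitivity analysis of all randomised and dosed infants in which a missing Day 180 assessment counts as non-response. Apply the same rule to control infants wherever their number at baseline is known. Where it is not, add a tipping-point analysis that varies the outcomes of missing infants in both the treated and control groups.
2. Limit the exclusion analysis to drop-outs for reasons other than progression, ulceration or safety, so that infants classed as failures under items 2 to 4 remain failures. This also removes the dependence on the two undefined terms.

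In Section 10.4.1:

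3. Describe the primary set as modified intent-to-treat and refer to the Day 30 rule.

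The cost is revised wording, one extra table (plus the tipping-point display if control denominators are unknown), and a supporting figure that will usually be less favourable to timolol. No additional data collection is needed in the treated arms.
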